7.1.3.2 Pharmacokinetic/Pharmacodynamic Evaluations

The decision as to which plasma samples collected will be assayed for evaluation of pharmacokinetics/pharmacodynamics will be collaboratively determined by the Department of Quantitative Pharmacology and Pharmacometrics (QP2) and Translational Pharmacology. If indicated, these samples may also be assayed and/or pooled for assay in an exploratory manner for metabolites and/or additional pharmacodynamic markers.

7.1.3.2.1 Blood Collection for Plasma MK-4250

Sample collection, storage and shipment instructions for plasma samples will be provided in the Study Operations Manual.

7.1.3.2.2 Blood Collection for HIV-1 Viral RNA and Viral Resistance

Sample collection, storage and shipment instructions for these blood samples will be provided by the site's local laboratory.

7.1.3.3 Planned Genetic Analysis Sample Collection

Sample collection, storage and shipment instructions for Planned Genetic Analysis samples will be provided in the Study Operations Manual.

7.1.3.4 Future Biomedical Research Samples

The following specimens are to be obtained as part of Future Biomedical Research:

- DNA for future research
- Leftover main study plasma from MK-4250 assay stored for future research
- Leftover main study plasma from HIV RNA and viral resistance assays stored for future use

7.1.4 Other Procedures

7.1.4.1 Withdrawal/Discontinuation

The investigator or trial coordinator must notify the Sponsor when a subject has been discontinued/withdrawn from the trial. If a subject discontinues for any reason at any time during the course of the trial, the subject may be asked to return to the clinic (or be contacted) for a post-trial visit (approximately 14 days after the last dose of trial drug is given) to have the applicable procedures conducted. However, the investigator may decide to perform the post-trial procedures at the time of discontinuation or as soon as possible after discontinuation. If the post-trial visit occurs prior to 14 days after the last dose of trial drug is given, the investigator should perform a follow-up phone call 14 days after the last dose of trial drug to determine if any adverse events have occurred since the post-trial clinic visit. Any adverse events which are present at the time of discontinuation/withdrawal should be

followed in accordance with the safety requirements outlined in Section 7.2 - Assessing and Recording Adverse Events.

7.1.4.1.1 Withdrawal From Future Biomedical Research

Subjects may withdraw their consent for Future Biomedical Research. Subjects may withdraw consent at any time by contacting the principal investigator for the main trial. If medical records for the main trial are still available, the investigator will contact the Sponsor using the designated mailbox ([contact]). Subsequently, the subject's consent for Future Biomedical Research will be withdrawn. A letter will be sent from the Sponsor to the investigator confirming the withdrawal. It is the responsibility of the investigator to inform the subject of completion of withdrawal. Any analyses in progress at the time of request for withdrawal or already performed prior to the request being received by the Sponsor will continue to be used as part of the overall research trial data and results. No new analyses would be generated after the request is received.

In the event that the medical records for the main trial are no longer available (e.g., if the investigator is no longer required by regulatory authorities to retain the main trial records) or the specimens have been completely anonymized, there will no longer be a link between the subject's personal information and their specimens. In this situation, the request for specimen withdrawal cannot be processed.

7.1.4.1.2 Lost to Follow-up

If a subject fails to return to the clinic for a required study visit and/or if the site is unable to contact the subject, the following procedures are to be performed:

- The site must attempt to contact the subject and reschedule the missed visit. If the subject is contacted, the subject should be counseled on the importance of maintaining the protocol-specified visit schedule.
- The investigator or designee must make every effort to regain contact with the subject at each missed visit (e.g. phone calls and/or a certified letter to the subject's last known mailing address or locally equivalent methods). These contact attempts should be documented in the subject's medical record.
- Note: A subject is not considered lost to follow up until the last scheduled visit for the individual subject. The amount of missing data for the subject will be managed via the pre-specified data handling and analysis guidelines.

7.1.4.2 Subject Blinding/Unblinding

This is an open label trial; there is no blinding for this trial.

7.1.4.3 Domiciling

Subjects will report to the clinical research unit (CRU) the evening prior to the scheduled day of trial drug administration and remain in the unit until 24 hours post-dose. At the discretion of the investigator, subjects may be requested to remain in the CRU longer.

7.1.4.4 Calibration of Critical Equipment

The investigator or qualified designee has the responsibility to ensure that any critical device or instrument used for a clinical evaluation/test during a clinical trial that provides important information about inclusion/exclusion criteria and/or safety or efficacy parameters shall be suitably calibrated and maintained to ensure that the data obtained is reliable and/or reproducible. Documentation of equipment calibration must be retained as source documentation at the trial site.

Critical Equipment for this trial includes:

- Equipment for taking VS
- ECG equipment and electrodes
- Equipment (including freezers) for the PK and PD samples

7.1.5 Visit Requirements

Visit requirements are outlined in Section 6.0 - Trial Flow Chart. Specific procedure-related details are provided above in Section 7.1 - Trial Procedures.

7.1.5.1 Screening

Approximately 4 weeks prior to treatment allocation, potential subjects will be evaluated to determine that they fulfill the entry requirements as set forth in Section 5.1.

Subjects may be rescreened after consultation with the Sponsor. Rescreening should include all screening procedures listed in the protocol flow chart, including consent review. Rescreen procedures cannot be conducted the day prior to treatment allocation if there are Day -1 procedures planned per protocol.

7.1.5.2 Treatment Period (All Panels)

Subjects will report to the CRU the day prior to the scheduled day of dosing or at a time specified by the investigator. Subjects will fast from all food and drink, except for water, for a minimum of 8 hours prior to study drug administration and prior to obtaining samples for laboratory safety tests.

After the Day 1 predose procedures have been completed, subjects will be assigned a unique allocation number associated with a specific study treatment as defined by a computer-generated allocation schedule. All subjects in each panel will be administered a single dose of MK-4250 in the morning. The exact clock time of dosing should be recorded.

7.1.5.3 Post-Trial

Subjects will be required to return to the clinic at least 14 days (+2 days) after the last dose of trial drug for the post-trial visit.

7.1.5.4 Critical Procedures Based on Trial Objectives: Timing of Procedure

For this trial, the blood samples for plasma MK-4250 and HIV-1 viral RNA data are the critical procedures.

At any post-dose timepoint, the blood sample for MK-4250 and the blood sample for viral RNA need to be collected as close to the exact timepoint as possible. All other procedures should be completed as close to the prescribed/scheduled time as possible. Trial procedures can be performed prior or after the prescribed/scheduled time.

The order of priority can be changed during the trial with joint agreement of the investigator and the Sponsor Clinical Director.

Any nonscheduled procedures required for urgent evaluation of safety concerns take precedence over all routine scheduled procedures.

The following variance in procedure collection times will be permitted.

- Blood collection for PK and PD as outlined in [Table 11](#) below

Table 11 Plasma PK and HIV RNA - Blood Collection Windows

PK/PD collection	PK/PD Collection Window
0 to < 1 hr	5 min
1 to < 24 hr	15 min
24 to < 48 hr	2 hr
48 to 168 hr	3 hr
> 168 hr	24 hr

- Predose standard safety evaluations: vital signs & ECG 3 hrs; laboratory safety tests including drug screen & physical exam 24 hrs
- Postdose standard safety evaluations (vital signs, ECG, laboratory safety tests, physical exam) as outlined in [Table 12](#) below.

Table 12 Postdose Scheduled Time – Data Collection Windows

Scheduled Time	Data Collection Window
0 to < 24 hr	30 min
24 to <48 hr	2 hr
48 to 168 hr	3 hr

7.1.5.5 Trial Design/Dosing/Procedures Modifications Permitted within Protocol Parameters

This is a Phase I assessment of MK-4250 in humans, and the pharmacokinetic, pharmacodynamic and safety profiles of the compound is still being elucidated. This protocol is written with some flexibility to accommodate the inherent dynamic nature of Phase I clinical trials. Modifications to the dose, dosing regimen and/or clinical or laboratory procedures currently outlined below may be required to achieve the scientific goals of the trial objectives and/or to ensure appropriate safety monitoring of the trial subjects.

As such, some alterations from the currently outlined dose and/or dosing regimen may be permitted based on newly available data, but the maximum daily dose may not exceed those currently outlined in the protocol.

- Repeat of or decrease in the dose of the trial drug administered in any given panel
- Entire panel(s) may be omitted
- Addition of a study pause
- Instructions to take trial drug with or without food or drink may also be modified based on newly available data
- Composition of the meal taken with the trial drug may also be modified based on newly available data
- Modification of the PK/PD sample processing and shipping details based on newly available data

The pharmacokinetic/pharmacodynamic sampling scheme currently outlined in the protocol may be modified during the trial based on newly available pharmacokinetic or pharmacodynamic data (e.g., to obtain data closer to the time of peak plasma concentrations) but the number of samples will not increase. If indicated, these collected samples may also be assayed in an exploratory manner for metabolites and/or additional pharmacodynamic markers.

Up to additional 50 mL of blood may be drawn for safety, pharmacokinetic, and/or pharmacodynamic analyses. The total blood volume withdrawn from any single subject will not exceed the maximum allowable volume during his/her participation in the entire trial (Section 12.3).

The timing of procedures for assessment of safety procedures (e.g., vital signs, ECG, safety laboratory tests, etc.) currently outlined in the protocol may be modified during the trial based on newly available safety, tolerability, pharmacokinetic or pharmacodynamic data (e.g., to obtain data closer to the time of peak plasma concentrations). Additional laboratory safety tests may be added to blood samples previously drawn to obtain additional safety information (e.g., adding creatinine kinase to serum chemistry panel that was already drawn). These changes will not increase the number of trial procedures for a given subject during his/her participation in the entire trial.

It is understood that the current trial may employ some or none of the alterations described above. Any alteration made to this protocol to meet the trial objectives must be detailed by

the Sponsor in a letter to the Trial File and forwarded to the investigator for retention. The letter may be forwarded to the IRB/IEC at the discretion of the investigator.

If an alteration impacts subject safety, affects the scientific value of the study results, and/or significantly alters the execution of the trial, a notification will be submitted prior to proceeding with the trial. If approved, enrollment and dosing may restart at that time.

7.2 Assessing and Recording Adverse Events

An adverse event is defined as any untoward medical occurrence in a patient or clinical investigation subject administered a pharmaceutical product and which does not necessarily have to have a causal relationship with this treatment. An adverse event can therefore be any unfavourable and unintended sign (including an abnormal laboratory finding, for example), symptom, or disease temporally associated with the use of a medicinal product or protocol-specified procedure, whether or not considered related to the medicinal product or protocol-specified procedure. Any worsening (i.e., any clinically significant adverse change in frequency and/or intensity) of a preexisting condition that is temporally associated with the use of the Sponsor's product, is also an adverse event.

Changes resulting from normal growth and development that do not vary significantly in frequency or severity from expected levels are not to be considered adverse events. Examples of this may include, but are not limited to, teething, typical crying in infants and children and onset of menses or menopause occurring at a physiologically appropriate time.

Sponsor's product includes any pharmaceutical product, biological product, device, diagnostic agent or protocol-specified procedure, whether investigational (including placebo or active comparator medication) or marketed, manufactured by, licensed by, provided by or distributed by the Sponsor for human use.

Adverse events may occur during clinical trials, or as prescribed in clinical practice, from overdose (whether accidental or intentional), from abuse and from withdrawal.

For randomized subjects only, all adverse events that occur after the consent form is signed but before treatment allocation/randomization must be reported by investigator if they are the result of a protocol-specified intervention, including but not limited to washout or discontinuation of usual therapy, diet, placebo treatment or a procedure. From the time of treatment allocation/randomization through 14 days following cessation of treatment, all adverse events must be reported by the investigator. Such events will be recorded at each examination on the Adverse Event case report forms/worksheets. The reporting timeframe for adverse events meeting any serious criteria is described in section 7.2.3.1. The investigator will make every attempt to follow all subjects with non-serious adverse events for outcome.

Electronic reporting procedures can be found in the Electronic Data Capture (EDC) data entry guidelines. Paper reporting procedures can be found in the Investigator Trial File Binder (or equivalent).

7.2.1 Definition of an Overdose for This Protocol and Reporting of Overdose to the Sponsor

The subject has taken (accidentally or intentionally) any drug administered as part of the protocol and exceeding the dose as prescribed by the protocol. It is up to the investigator or the reporting physician to decide whether a dose is to be considered an overdose, in consultation with the Sponsor.

If an adverse event(s) is associated with (“results from”) the overdose of Sponsor's product or vaccine, the adverse event(s) is reported as a serious adverse event, even if no other seriousness criteria are met.

If a dose of Sponsor's product or vaccine meeting the protocol definition of overdose is taken without any associated clinical symptoms or abnormal laboratory results, the overdose is reported as a non-serious Event of Clinical Interest (ECI), using the terminology “accidental or intentional overdose without adverse effect.”

All reports of overdose with and without an adverse event must be reported by the investigator within 24 hours to the Sponsor either by electronic media or paper. Electronic reporting procedures can be found in the EDC data entry guidelines. Paper reporting procedures can be found in the Investigator Trial File Binder (or equivalent).

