1.0 TRIAL SUMMARY

Abbreviated Title	MK-4250 Single Dose Trial in HIV-1 Infected Subjects
Sponsor Product Identifiers	MK-4250
Trial Phase	Ib
Clinical Indication	Treatment of HIV-1 Infection
Trial Type	Interventional
Type of control	No treatment control
Route of administration	Oral
Trial Blinding	Unblinded Open-label
Treatment Groups	Up to 5 panels (Panels A, B, D, E and F) of 6 subjects each will receive a single dose of MK-4250. Panel C has been removed per this amendment. Panel A: 150 mg Panel B: 600 mg Panel D: 900 mg Panel E: ≤ 900 mg, with low fat meal Panel F: ≤ 900 mg, with moderate fat meal
Number of trial subjects	Approximately 30 subjects will be enrolled.
Estimated duration of trial	The Sponsor estimates that the trial will require approximately 10 months from the time the first subject signs the informed consent until the last subject's last study-related phone call or visit.
Duration of Participation	Each subject will participate in the trial for approximately 6 weeks from the time the subject signs the Informed Consent Form (ICF) through the final contact. After a screening phase of 4 weeks, each subject will receive a single dose of study medication. After dosing, each subject will be followed for 14 days.

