- k. For all subjects, the post-trial visit should occur approximately 14 days (+2 days) following administration of the study drug.
- l. For all subjects, blood for HIV-1 viral RNA and viral resistance will be collected at timepoints up to the initiation of ART. For subjects who do not initiate follow on ART, blood for HIV-1 viral RNA and viral resistance will continue to be collected until the post trial visit. Ultra-deep sequencing (UDS) may be performed if viral resistance cannot be measured due to low viral load. At the timepoint immediately preceding initiation of ART, a portion of the blood collected for viral resistance testing will be sent to Labor Berlin for extraction of proviral DNA. This proviral DNA will be frozen and analyzed for the presence of viral resistance mutations only if standard Sanger sequencing cannot be performed because plasma viral load is too low at this timepoint.
- m. The predose PE and laboratory assessments (including drug screen) may be performed within 24 hour prior to dosing.
- n. The 72 hour post-dose PK sample will be drawn only for the first 3 subjects enrolled in Panel B; in addition, the 240 hr timepoint will not be drawn for these three subjects.
- o. For Panels E and F only, a dosing breakfast will be provided at approximately 30 mins pre-dose on Day 1.

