7.2.3 Immediate Reporting of Adverse Events to the Sponsor

7.2.3.1 Serious Adverse Events

A serious adverse event is any adverse event occurring at any dose or during any use of Sponsor's product that:

- Results in death;
- Is life threatening;
- Results in persistent or significant disability/incapacity;
- Results in or prolongs an existing inpatient hospitalization;
- Is a congenital anomaly/birth defect;
- Is an other important medical event.

Note: In addition to the above criteria, adverse events meeting either of the below criteria, although not serious per ICH definition, are reportable to the Sponsor in the same timeframe as SAEs to meet certain local requirements. Therefore, these events are considered serious by the Sponsor for collection purposes.

- Is a cancer;
- Is associated with an overdose.

Refer to [Table 13](#) for additional details regarding each of the above criteria.

For the time period beginning when the consent form is signed until treatment allocation/randomization, any serious adverse event, or follow up to a serious adverse event, including death due to any cause, that occurs to any subject must be reported within 24 hours to the Sponsor if it causes the subject to be excluded from the trial, or is the result of a protocol-specified intervention, including but not limited to washout or discontinuation of usual therapy, diet, placebo treatment or a procedure.

For the time period beginning at treatment allocation/randomization through 14 days following cessation of treatment, any serious adverse event, or follow up to a serious adverse event, including death due to any cause, whether or not related to the Sponsor's product, must be reported within 24 hours to the Sponsor either by electronic media or paper. Electronic reporting procedures can be found in the EDC data entry guidelines. Paper reporting procedures can be found in the Investigator Trial File Binder (or equivalent).

Additionally, any serious adverse event, considered by an investigator who is a qualified physician to be related to the Sponsor's product that is brought to the attention of the investigator at any time outside of the time period specified in the previous paragraph also must be reported immediately to the Sponsor.

All subjects with serious adverse events must be followed up for outcome.

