7.2.3.2 Events of Clinical Interest

Selected non-serious and serious adverse events are also known as Events of Clinical Interest (ECI) and must be reported to the Sponsor.

For the time period beginning when the consent form is signed until treatment allocation/randomization, any ECI, or follow up to an ECI, that occurs to any subject must be reported within 24 hours to the Sponsor if it causes the subject to be excluded from the trial, or is the result of a protocol-specified intervention, including but not limited to washout or discontinuation of usual therapy, diet, placebo treatment or a procedure.

For the time period beginning at treatment allocation/randomization through 14 days following cessation of treatment, any ECI, or follow up to an ECI, whether or not related to the Sponsor's product, must be reported within 24 hours to the Sponsor, either by electronic

media or paper. Electronic reporting procedures can be found in the EDC data entry guidelines. Paper reporting procedures can be found in the Investigator Trial File Binder (or equivalent).

Events of clinical interest for this trial include:

1. an overdose of Sponsor's product, as defined in Section 7.2.1 - Definition of an Overdose for This Protocol and Reporting of Overdose to the Sponsor, that is not associated with clinical symptoms or abnormal laboratory results.
2. an elevated AST or ALT lab value that is greater than or equal to 3X the upper limit of normal and an elevated total bilirubin lab value that is greater than or equal to 2X the upper limit of normal and, at the same time, an alkaline phosphatase lab value that is less than 2X the upper limit of normal, as determined by way of protocol-specified laboratory testing or unscheduled laboratory testing.*

*Note: These criteria are based upon available regulatory guidance documents. The purpose of the criteria is to specify a threshold of abnormal hepatic tests that must trigger an additional evaluation for an underlying etiology. The trial site guidance for assessment and follow up of these criteria can be found in the Investigator Trial File Binder (or equivalent).

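### Mandatory reporting of AEs, unrelated SAEs and ECIs ends 14 days after the single dose, but the last safety visit may fall up to 2 days later, leaving a gap of at most 48 hours

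*Combined protocol and SAP*

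**What the plan says.** **Reporting window.** For adverse events, Section 7.2 says: "From the time of treatment allocation/randomization through 14 days following cessation of treatment, all adverse events must be reported by the investigator". Section 7.2.3.1 sets the same end point for SAEs of any cause: "For the time period beginning at treatment allocation/randomization through 14 days following cessation of treatment, any serious adverse event". Section 7.2.3.2 does so for ECIs: "For the time period beginning at treatment allocation/randomization through 14 days following cessation of treatment, any ECI, or follow up to an ECI". Section 7.2.3.1 then adds an open-ended rule: an SAE that a physician investigator considers related, and that comes to notice "at any time outside of the time period specified in the previous paragraph also must be reported immediately to the Sponsor". Non-serious AEs, unrelated SAEs and ECIs have no comparable extension. Section 7.2.2 applies the same 14-day limit to pregnancy and lactation.

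**Treatment.** Section 1.0 says that "each subject will receive a single dose of study medication", so treatment ends with the Day 1 dose.

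**Last visit.** Section 7.1.5.3 says: "Subjects will be required to return to the clinic at least 14 days (+2 days) after the last dose of trial drug". Footnote k of the flow chart in Section 6.0 says that "the post-trial visit should occur approximately 14 days (+2 days) following administration of the study drug". In the 336 h/post-trial column the flow chart marks physical examination, ECG, vital signs, haematology, chemistry, urinalysis and the end of the AE monitoring row.

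**Early visits.** For a discontinued subject whose post-trial visit takes place before day 14, Section 7.1.4.1 asks for a telephone call at 14 days to pick up later adverse events. There is no matching rule for a visit after day 14.

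**The concern.** The visit window and the reporting window share a boundary at 14 days, and the whole of the visit's stated 2-day tolerance lies beyond it. A subject can therefore attend on time under Sections 6.0 and 7.1.5.3 and still be examined after the reporting duty has lapsed.

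Safety and tolerability is a primary objective, and this visit holds the only scheduled safety laboratory tests after 168 h. Section 4.2.3.1 singles out liver tests because of the dog findings and shows the same double clock: it has them monitored to 14 days after the last dose and also until the post-study visit. A liver-test ECI is defined by measured values and calls for notification within 24 hours. For an ECI arising in the gap, that duty would depend on which permitted day the subject attended. Halting rule 3 in Section 5.11 also counts severe laboratory abnormalities with a potential causal relationship. A severe but non-serious abnormality arising in the gap could bear on that rule without a mandatory duty to report it.

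**Working it through.** The plan gives no figure of its own to reproduce. The check sets the two windows side by side.

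**Inputs**
- Dose: single, on Study Day 1 (Sections 1.0 and 5.2).
- End of reporting: 14 days after treatment ends (Sections 7.2, 7.2.3.1, 7.2.3.2).
- Post-trial visit: 14 days, +2 days (Section 6.0 footnote k; Section 7.1.5.3).
- Related SAEs: no end date (Section 7.2.3.1).

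**Step 1, end of reporting.** 14 × 24 = 336 h. Study Day = 1 + 14 = 15, which is the flow chart's own label for 336 h.

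**Step 2, visit window.** Earliest: 14 × 24 = 336 h (Study Day 15). Latest: (14 + 2) × 24 = 384 h (Study Day 1 + 16 = 17).

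**Step 3, gap.** 384 − 336 = 48 h. A visit on Study Day 15 is covered, because the 14-day limit is inclusive. Visits on Study Days 16 and 17 are not.

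**Step 4, what happens to an event with onset after 336 h, found at a visit on Study Day 16 or 17**

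| Event or data | Status under the text |
|---|---|
| Non-serious AE | No mandatory report (7.2) |
| SAE judged unrelated | No mandatory report (7.2.3.1) |
| ECI, including the liver-test ECI, that is not a related SAE | No mandatory report (7.2.3.2) |
| SAE judged related | Reportable immediately, at any time (7.2.3.1) |
| Laboratory, ECG and vital-sign values | Collected (6.0) and within the planned safety endpoints and summaries (8.2.2, 8.2.4) |

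**Step 5, weight of the visit.** From the flow chart, post-dose safety laboratory tests are at 24, 168 and 336 h, so this visit supplies 1 of 3 sets. Post-dose ECGs are at 4, 24, 168 and 336 h, so it supplies 1 of 4.

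**Step 6, number of subjects affected.** The documents give no attendance dates within the visit window. The number is zero if everyone attends on Study Day 15, and no expected share can be derived.

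**The case against.** The strongest reply is that nothing of substance is lost. The flow chart carries AE monitoring through the post-trial visit, and Section 7.2 has events recorded at each examination. A mandatory minimum does not forbid reporting more, so sites would probably record what they find. The visit is scheduled at 336 h, Section 1.0 plans 14 days of follow-up, and Section 7.1.5.4 asks for procedures close to schedule. With half-lives of 35.9 h (Table 2, 150 mg) to about 47 h (Section 4.1.1), 336 h is 336/47 = 7.1 to 336/35.9 = 9.4 half-lives, so little drug should remain. Most of this stands, and it makes the impact small. It does not remove the conflict: the recording sentence in 7.2 refers back to events inside the 14-day window, and probable good practice is not a duty.

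Four stronger readings are tempting, and the documents do not support them:
- *Late findings drop out of the analysis.* Section 8.2.2 makes laboratory tests, ECGs and vital signs safety endpoints in their own right, and Section 8.2.4 sets no 14-day cut-off.
- *All SAE reporting stops at day 14.* Related SAEs remain reportable without limit.
- *Anything first seen at a late visit is outside the window.* The text does not say whether onset or detection counts. An event with onset by 336 h but disclosed later can be read as inside. For a laboratory abnormality, though, a sample taken on Study Day 16 or 17 cannot by itself show that onset was earlier.
- *Most final assessments fall outside.* An even spread over three days would give two thirds, but nothing supports an even spread, and the possible range is 0 to 100%.

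**Conclusion.** Wrong as written: an internal conflict with minor impact. The reporting sections stop at 336 h, while the visit window and the flow chart's AE monitoring can run to 384 h. The gap is at most 48 h per subject. It affects only non-serious AEs, SAEs judged unrelated and ECIs with onset after 336 h, and only in subjects who attend on Study Day 16 or 17. This rests on two readings: that treatment ends with the single Day 1 dose, and that the 14-day limit includes a visit at 336 h. The defect is a mismatch of wording, not an absence of monitoring, and the number of subjects affected is unknown.

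**What to change.** In Sections 7.2, 7.2.3.1 and 7.2.3.2, end the reporting window at *the later of 14 days after dosing or completion of the post-trial visit*. Make the same change in Section 7.2.2, because β-hCG is tested at that visit and the same 14-day limit applies there.

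The *later of* form matters. Ending the window simply at the post-trial visit could close it early for a discontinued subject seen before day 14, and would undercut the day-14 telephone call in Section 7.1.4.1. With the window running to completion of the visit, the question of onset or detection no longer matters for what is found there.

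Section 8.2.4 needs no change. The cost is one phrase in four sections and up to 2 more days of reporting per subject, with no added visits or samples.
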